5.5 Clinically notable vital signs

The criteria for clinically notable abnormalities are defined as follows:

Clinically notable elevated values

- Systolic blood pressure of $> 140 \text{ mmHg}$ (hypertension)
- Diastolic blood pressure of $> 90 \text{ mmHg}$ (hypertension)
- Pulse rate $> 100 \text{ bpm}$ (tachycardia).

Clinically notable below normal values

- Systolic blood pressure of $< 90 \text{ mmHg}$ (hypotension)
- Diastolic blood pressure of $< 60 \text{ mmHg}$ (hypotension)
- Pulse rate $< 60 \text{ bpm}$ (bradycardia)

Worsening clinically notable vital signs

- High pulse rate [bpm]: $\geq 100 \text{ bpm}$ with increase from Baseline of $\geq 15 \text{ bpm}$; low pulse rate [bpm]: $\leq 60 \text{ bpm}$ with decrease from Baseline of $\geq 15 \text{ bpm}$.
- High systolic blood pressure [mmHg]: $\geq 140 \text{ mmHg}$ with increase from Baseline of $\geq 20 \text{ mmHg}$; Low systolic blood pressure [mmHg]: $\leq 90 \text{ mmHg}$ with decrease from Baseline of $\geq 20 \text{ mmHg}$.
- High diastolic blood pressure [mmHg]: $\geq 90 \text{ mmHg}$ with increase from Baseline of $\geq 15 \text{ mmHg}$; Low diastolic blood pressure [mmHg]: $\leq 60 \text{ mmHg}$ with decrease from Baseline of $\geq 15 \text{ mmHg}$.

5.6 Statistical models

5.6.1 SAS code

The below SAS code will used for statistical value.

Frequency and proportion:

```
proc freq data = <.....>;
    tables trt*response_variable/ chisq;
run;
```

trt=treatment group

response_variable=Gender, Age group, Race, Country, ASAS40, ASAS20, ASASPR, BASDAI 50 etc.

Summary Statistics:

Univariate procedure will be used for continuous response.

```
proc univariate data=<.....>;  
    var response_variable;  
    by trtn;  
    output out=<.....> n=_n mean=_mean std=_sd min=_min median=_med  
          max=_max;  
run;
```

response_variable= Age, height, weight, bmi etc.

Multivariate logistic regression

```
ods output oddsratios=ratio parameterestimates=est diffs=diff LSMeans=lsmean;  
proc logistic data=<.....>;  
    class treatment (ref='1') center /param=glm;  
    model respl(event='1')= treatment center base_crp base_weight /cl ;  
    oddsratio treatment;  
    lsmeans treatment / diff oddsratio cl;  
run;
```

Mixed-Effect Model Repeated Measures (MMRM):

```
proc mixed data=<.....>;  
    class treatment subject visit;  
    model chg= treatment visit base_var weight treatment*visit base_var*visit;  
    repeated visit/ subject= subject (treatment ) type=un r rcorr;  
    lsmeans treatment*visit / pdiff cl slice=visit;  
run;
```

Using the slice option above means that the difference between treatment cohorts will be tested for each visit.

Multiple Imputation

Impute the missing values 100 times (NIMPUTE) with a seed=457<studycode> as shown below:

```
proc mi data=<xxxxx> out=<impxx> minmaxiter=100000 nimpute=100 seed=4572320;  
    by trt;  
    var WEIGHT STRATA var1_base var1_week1-var1_week104;  
    mcmc chain=multiple initial=em;  
run;
```

CM medication categories from CM source dataset

1. NSAIDs

CMCAT = 'NONSTEROIDAL ANTI-INFLAMMATORY DRUGS' and
ATC2= 'ANTIINFLAMMATORY AND ANTIRHEUMATIC PRODUCTS' and
ATC3= 'ANTIINFLAMMATORY AND ANTIRHEUMATIC PRODUCTS, NON-STEROIDS' ;

2. Other axSpA medication

a) CMCAT = 'OTHER AXIAL SPONDYLOARTHRITIS MEDICATION' and
ATC4 in ('PYRAZOLONES', 'OTHER ANTIMIGRAINE PREPARATIONS', 'ANILIDES')
b) CMCAT = 'OTHER AXIAL SPONDYLOARTHRITIS MEDICATION' and ATC2 = 'ANALGESICS' and
ATC3 = 'OPIOIDS' .

c) CMCAT = 'OTHER AXIAL SPONDYLOARTHRITIS MEDICATION'
and ATC4 in ('OTHER ANTIMIGRAINE PREPARATIONS', 'OTHER CENTRALLY ACTING AGENTS',
'OTHER ANALGESICS AND ANTI PYRETICS', 'OTHER ANTIMIGRAINE PREPARATIONS', 'SELECTIVE
SEROTONIN REUPTAKE INHIBITORS', 'CARBAMIC ACID ESTERS');

3. DMARds

- a) CMCAT = 'CONVENTIONAL SYSTEMIC DMARD(s)' and ATC4 = 'SELECTIVE
IMMUNOSUPPRESSANTS' and CMSCAT = 'Standard of care of medication_CMS004'.
- b) CMCAT = 'CONVENTIONAL SYSTEMIC DMARD(s)' and ATC4 = 'OTHER ANTIINFLAMMATORY AND
ANTIRHEUMATIC AGENTS, NON-STEROIDS'.
- c) CMCAT = 'CONVENTIONAL SYSTEMIC DMARD(s)' and ATC4 = 'OTHER IMMUNOSUPPRESANTS'
- d) CMCAT = 'CONVENTIONAL SYSTEMIC DMARD(s)' and ATC4 = 'SELECTIVE
IMMUNOSUPPRESSANTS' and CMSCAT = 'Prior axSpa medication_CMS002'.

4. bDMARD

- a) CMCAT = 'BIOLOGICAL DMARD' and ATC4 = 'INTERLEUKIN INHIBITORS'.
- b) CMCAT = 'BIOLOGICAL DMARD' and ATC4 = 'TUMOR NECROSIS FACTOR ALPHA (TNF-) INHIBITORS'.

5. Glucocorticodis

- a) CMCAT= 'GLUCOCORTICOIDS' and CMROUTE in ('ORAL', 'INTRAMUSCULAR', 'INTRAVENOUS')
and ATC4 = 'GLUCOCORTICOIDS'
- b) CMCAT= 'GLUCOCORTICOIDS' and CMROUTE = 'INTRA-ARTICULAR'

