5.3 Concomitant medication grouping

The following concomitant medications will be categorized by the classes below.

- 1. Nonsteroidal anti-inflammatory drugs (NSAIDs):** Celecoxib, diclofenac, ibuprofen, etoricoxib, meloxicam, naproxen, indometacin, parecoxib, acemetacin, aceclofenac, piroxicam, dexketoprofen, nabumetone, rofecoxib, lornoxicam, diclofenac sodium, ketoprofen, flurbiprofen, piroxicam betadex, sulindac, naproxen sodium, niflumic acid, tenoxicam.

2. Other axSpA medication(s):

Analgesics		
A) Non-opioid	B) Opioid	(C) Other
Metamizole, metamizole sodium, naloxone hydrochloride, caffeine, papaver somniferum latex, paracetamol, paracetamol, flupirtine maleate, flupirtine maleate	Naloxone hydrochloride; tilidine hydrochloride, codeine, morphine sulfate, codeine phosphate, oxycodone, tramadol, tramadol hydrochloride	Tizanidine hydrochloride, amitriptyline hydrochloride, methocarbamol, amitriptyline, pregabalin, citalopram, methocarbamol

3. DMARDs:

ts DMARDs	cs DMARDs		
JAKi	SS	MTX	Other
Upadacitinib	Sulfasalazine	Methotrexate sodium	Leflunomide

4. Biological DMARDs:

(A) aIL-17	(B) TNFi	(C) Other
Secukinumab, ixekizumab	Golimumab, adalimumab, etanercept, certolizumab pegol, infliximab, adalimumab biosimilar	Ustekinumab

5. Glucocorticoids:

(A) Systemic steroids (oral, iv, im)	(B) Intraarticular steroids
Prednisolone, cortisone acetate, prednisone, triamcinolone, dexamethasone, prednisolone acetate, cortisone	Cortisone acetate, triamcinolone, prednisolone acetate, triamcinolone hexacetonide

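### The medication-class filters in SAP 5.6.1 do not implement the substance-based groups of SAP 5.3, so some rows of the descriptive class tables could be mislabelled

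*SAP*

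**What the plan says.** SAP 5.3 introduces its groups with "The following concomitant medications will be categorized by the classes below" and then lists substances under each class. Upadacitinib is the targeted synthetic DMARD (JAKi). Sulfasalazine, methotrexate and leflunomide are conventional DMARDs, with leflunomide under Other. Biologics have three groups: (A) anti-IL-17, given as "Secukinumab, ixekizumab"; (B) TNF inhibitors; and (C) Other, given as ustekinumab.

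SAP 5.6.1 gives the filters to be run on the concomitant-medication dataset. In the DMARD block, lines a) and d) both require the conventional-DMARD category and the ATC4 term SELECTIVE IMMUNOSUPPRESSANTS. Line a) ends "IMMUNOSUPPRESSANTS' and CMSCAT = 'Standard of care of medication_CMS004" and line d) ends "IMMUNOSUPPRESSANTS' and CMSCAT = 'Prior axSpa medication_CMS002". Lines b) and c) carry no `CMSCAT` condition. The biologic block has two lines: "a) CMCAT = 'BIOLOGICAL DMARD' and ATC4 = 'INTERLEUKIN INHIBITORS" and "CMCAT = 'BIOLOGICAL DMARD' and ATC4 = 'TUMOR NECROSIS FACTOR ALPHA (TNF-) INHIBITORS". Among the analgesic filters, line 2a uses "ATC4 in ('PYRAZOLONES', 'OTHER ANTIMIGRAINE PREPARATIONS', 'ANILIDES", and OTHER ANTIMIGRAINE PREPARATIONS appears again in line 2c.

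SAP 2.4.1 promises a summary of all SOC-arm medications with their drug class. SAP 2.4.2 refers to Appendix 5.3 for the medication categories and, separately, plans tables by ATC and preferred term.

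**The concern.** A class rule should send a given drug to the same class wherever it was recorded. Here the line a drug reaches depends on the form it was entered on, and one class defined in 5.3 cannot be reached at all.

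This deserves attention because SOC treatment is left to the investigator. Protocol 6.2.2.2 prohibits no concomitant treatment in that arm, and Protocol 6.1 allows a switch to an IL-17 inhibitor after a first biologic fails. The class tables are therefore one of the ways a reader learns what the treat-to-target strategy was compared with. The anti-IL-17 row matters most, because it shows how far SOC patients received the class under test.

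**Working it through.** The plan states no figure on this point, so there is none to reproduce. The check is to trace test records through the 5.6.1 filters and compare the result with 5.3.

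**Two premises that the documents do not state.**
- The code lines carry no class labels. I match a) to d) with the column order of 5.3: JAKi, sulfasalazine, methotrexate, Other. Four lines against four columns makes this the natural reading. The `CMSCAT` condition appears only on a) and d), which looks like a device to separate two drugs sharing one ATC4 term.
- The ATC4 terms of the individual drugs are not given. I take upadacitinib and leflunomide both to carry SELECTIVE IMMUNOSUPPRESSANTS, as the code implies. For ustekinumab I try both possibilities.

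**DMARDs**

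| Record | Class in 5.3 | Line reached | Class by column order | Agrees? |
|---|---|---|---|---|
| Upadacitinib, SOC | JAKi | 3a | JAKi | yes |
| Upadacitinib, prior | JAKi | 3d | csDMARD Other | no |
| Leflunomide, SOC | csDMARD Other | 3a | JAKi | no |
| Leflunomide, prior | csDMARD Other | 3d | csDMARD Other | yes |
| Either drug, any other `CMSCAT` value | as above | none | none | no |

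The substance makes no difference to the line reached; only `CMSCAT` does.

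**Biologics**

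| Record | Class in 5.3 | Line reached | Agrees? |
|---|---|---|---|
| Ustekinumab, ATC4 = interleukin inhibitors | (C) Other | 4a, the anti-IL-17 line | no |
| Ustekinumab, any other ATC4 outside 4a and 4b | (C) Other | none | no |

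There is no line 4c, so no record can reach (C). Line 4a also takes every interleukin inhibitor, whereas group (A) in 5.3 names two drugs.

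**Analgesics.** A record coded OTHER ANTIMIGRAINE PREPARATIONS satisfies both 2a (non-opioid) and 2c (other). It is counted in both groups if the lines are programmed as independent flags. If they are applied in sequence, it is counted once, in whichever group comes first. The SAP does not say which.

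**Where the result is used.** The classes serve the medication summaries: SAP 2.4.2 refers to 5.3, and I take the drug class in SAP 2.4.1 to be the same grouping, although that section does not say so. The logistic and MMRM models in SAP 2.5 and 2.7 do not use them. The adverse-event split of the SOC arm in SAP 2.8.1 is by named biologic and other, not by these classes.

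**The case against.** The strongest reply is that 5.3 is the controlling definition, since SAP 2.4.2 points to it, and that the 5.6.1 lines are only working filters. SAP 1 places further programming detail in dataset specifications and table shells, which are not among the documents. The `CMSCAT` split may also have fitted the data when the categories were added in amendment 3.0: if upadacitinib occurs only in SOC records and leflunomide only in prior records, both are sorted correctly. Inclusion criterion 9 and the leflunomide washout in Protocol Table 6-1 point that way, because they generate prior leflunomide records. An SOC leflunomide record needs a new start after randomization, while Protocol 6.1 describes a biologic, usually a TNF blocker, as the step after NSAID failure.

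This limits the likely consequence but does not remove the contradiction. The SAP does not state that condition, and new leflunomide in SOC is permitted. Nor does the argument help group (C), which has no line whatever the data.

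Two stronger readings are tempting. A reader might infer that all SOC leflunomide records are misclassified, or assume a usage rate and attach a patient count. Neither is supported: the line-to-class match and the ATC4 terms are inferred, and the documents give no usage figures. A reader might also infer that the SOC comparator as a whole would be misdescribed. That goes too far. SOC JAK inhibitors sort correctly under the same reading, the prior JAK-inhibitor error concerns prior medication rather than the comparator, and the preferred-term tables still show each drug by name, so anti-IL-17 use in SOC can be read there.

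**Conclusion.** Wrong as written, but minor and confined to descriptive tables. Three contradictions stand on the text: lines 3a and 3d separate drugs by record source where 5.3 separates them by substance; group (C) Other biologics has no code; and one ATC4 term belongs to two analgesic groups.

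The consequence is conditional. Class rows for SOC and for prior or concomitant medication could be mislabelled if the relevant records occur, and for the DMARD rows only if the column-order reading and the shared ATC4 term are right. The number of affected patients cannot be derived from the documents. The primary and secondary efficacy analyses and the tables by ATC and preferred term are unaffected.

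**What to change.** In SAP 5.6.1:

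- Classify DMARDs by the coded substance listed in 5.3 whatever the `CMSCAT` value: JAK inhibitors to tsDMARD/JAKi, leflunomide to csDMARD/Other.
- Limit line 4a to secukinumab and ixekizumab, and add a line 4c for other biologics.
- Assign each antimigraine-coded drug to one analgesic group by substance.

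Two checks belong in the same edit. The ATC4 term in line 3c appears as OTHER IMMUNOSUPPRESANTS; if that spelling is in the source file and not an effect of text extraction, an exact match to the correctly spelt term returns nothing. The glucocorticoid lines should keep their route condition, because 5.3 lists some of the same substances under both systemic and intra-articular use.

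The cost is a few lines of programming specification. No data collection, analysis set or model changes.
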